### **6.5 Anesthesia protocol for both intervention and control group**

- 1) During the study period (from preop to postop day 5), anticholinergics such as scopolamine are strictly prohibited; atropine or glycopyrrolate can only be used for treatment of bradycardia; the use of midazolam for anxiolysis is allowed but not encouraged;
- 2) In both arms, the anesthesia induction is per standard care using agents of lidocaine, propofol, sufentanyl and muscle relaxant. The administration of propofol in the intervention arm is via pump infusion and guided by SedLine.
- 3) The anesthesia is maintained using propofol infusion (0-200 mcg/kg/min) and remifentanyl infusion (0.05-0.2 mcg/min/kg). Sufentanyl and muscle relaxant boluses can be used during surgery.
- 4) The anesthetic adjustment in the control arm is per the conventional practice (EEG monitored but blinded to anesthesia team) and in the intervention arm per the **Supplemental remark 1. SedLine-Guided Intervention Flow Chart**.

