## 7.3 Postoperative data

- 1) PACU Delirium: Occurrence of delirium in PACU will be assessed using the CAM-ICU 30 mins after extubation and before PACU discharge.
- 2) Postoperative Delirium (POD): POD will be assessed twice daily (8:00-10:00 am, and 18:00-20:00 pm) for 5 days from postoperative day 1 to 5 or until the patient is discharged home if the patient stays in hospital < 5 days. CAM is used for delirium assessment if the patient is on the floor; otherwise, CAM-ICU is used if the patient is in the ICU. Investigators for POD assessment will be trained by a psychiatrist to use CAM and CAM-ICU before the trial is commenced.
- 3) Non-delirium Complications: Any complications occurred within the first 30 days after surgery (for example: cardiac events, cerebrovascular events, renal injury, GI complications, infections, etc.) will be documented. Patients will be assessed via phone call if they are discharged before day 30 after surgery.
- 4) Subjective Pain Score: It will be assessed at PACU and 24 hours after surgery using the Numeric Rating Scale (NRS) (an 11-point scale where 0 indicates no pain and 10 indicates the worst pain).
- 5) Subjective Sleep Quality: It will be assessed at 8:00 am during the first postoperative day using the NRS (an 11-point scale where 0 indicates the best possible sleep and 10 indicates the worst possible sleep).
- 6) Length of Hospital Stay: The readiness for discharge will be used as the last day of hospitalization.
- 7) All-cause 30-day Mortality: Patients or family members will be called for assessment.
- 8) Adverse Events: If an adverse event occurs during patient hospitalization, it will be followed up until its disappearance or therapy ends.

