## 9. Adverse events

### 9.1 Definition

- 1) An adverse event indicates any unpredictable, unfavorable medical event that is associated with any medical intervention and occurs during the study period. It can be related to the study protocol or otherwise. It can manifest as any uncomfortable signs (including abnormal laboratory findings), symptoms or transient morbidity;
- 2) Predicted adverse events in this study:
  - Tachycardia: heart rate > 100 beats per minute or, in case of a baseline value > 83 beats per minute, an increase of more than 20% from baseline;
  - Hypertension: systolic blood pressure > 160 mmHg or, in case of a baseline value > 133 mmHg, an increase of more than 20% from baseline;
  - Bradycardia: heart rate < 55 beats per minute or, in case of a baseline value < 69 beats per minute, a decrease of more than 20% from baseline (before study drug infusion);
  - Hypotension: systolic blood pressure < 95 mmHg or, in case of a baseline value < 119 mmHg, a decrease of more than 20% from baseline;

- Recall: the patient remembers the details of the event(s) that occurs during the period when the patient is under appropriate general anesthesia per standard of care.

Note: for heart rate and blood pressure, the average values measured before surgery are used as baseline values.

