## **11. Unmask of blinding**

For an individual patient, at the completion of the study (30 days after surgery), all data are checked to ensure its quality and input into the database, the database will be locked up and the blindness will be unmasked.

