## Flow chart of the study

	Screen	Recruitment	Intraoperative	Postoperative follow-up								
				PACU	D1	D2	D3	D4	D5	D6-discharge	D30±3	
Inclusion/exclusion criteria	X	X										
Informed consent	X											
Demographic data	X	X										
Preoperative diagnosis	X	X										
Previous medical history	X	X										
Physical examination	X	X										
Auxiliary examination	X	X										
MMSE	X	X										
Baseline CAM	X	X										
Anesthesia			X									
Study protocol execution		X	X	X	X	X	X	X	X	X	X	X
Delirium assessment*				X	X	X	X	X	X			
Adverse events				X	X	X	X	X	X	X		
NRS of severity of pain				X	X							
NRS of subjective sleep quality					X							
Use of other drugs				X	X	X	X	X	X	X		
Postoperative complications**				X	X	X	X	X	X	X		X
All-cause 30-day mortality												X

\*Delirium will be assessed at PACU and twice daily (8:00-10:00 am and 18:00-20:00 pm) during postoperative day 1 to 5.

\*\*Patients will be followed up until postoperative day 30.

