**Inclusion Criteria:**

Age $\geq$ 50 years	Y 	N 
ASA physical score I-III	Y 	N 
Scheduled to undergo elective laparoscopic surgery under general anesthesia with endotracheal intubation	Y 	N 
Able to undergo MMSE and CAM assessment	Y 	N 
Extubation expected after surgery	Y 	N 
Scheduled to stay in hospital > 3 days after surgery	Y 	N 

\*Subjects cannot be enrolled in the study if any one of the above is "N"

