**Record of adverse events**

An adverse event indicates any unpredictable, unfavorable medical event that is associated with any medical intervention and occurs during the study period. It can be related to the study or not.

A severe adverse event indicates any unpredictable medical events that lead to death, threat to life, prolonged length of stay in hospital, persistent disability or dysfunction, or other severe results.

Any adverse event should be followed up until it is completely resolved or therapy terminated.

**Is there any new adverse event within 24 hours after surgery:** Yes; No

**Is there any new severe adverse event within 3 days after surgery:** Yes; No

(Report form of severe adverse event see attached table)

	Start time	End time	Diagnostic evidence	Mode of occurrence	Is it severe adverse event?	Treatment 	Outcome 	Related to study?
Recall 				 Persistent  Transient	 Yes  No			 Yes  No
Hypotension 				 Persistent  Transient	 Yes  No			 Yes  No
Bradycardia 				 Persistent  Transient	 Yes  No			 Yes  No
Hypertension 				 Persistent  Transient	 Yes  No			 Yes  No
Tachycardia 				 Persistent  Transient	 Yes  No			 Yes  No
Hypoxemia 				 Persistent  Transient	 Yes  No			 Yes  No
Other:				 Persistent  Transient	 Yes  No			 Yes  No

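### The CRF adverse event page asks about new events for 24 hours, and severe ones for 3 days, while Section 7.3 and the flow chart run to discharge; the windows must be reconciled

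*Combined protocol and SAP*

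**What the plan says.** The Record of adverse events page of the CRF puts two yes/no questions above its event table: "Is there any new adverse event within 24 hours after surgery" and "Is there any new severe adverse event within 3 days after surgery". A pointer to the severe event report form follows the second.

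The protocol describes longer windows:

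- Section 7.3, item 8: "If an adverse event occurs during patient hospitalization, it will be followed up until its disappearance or therapy ends".
- Flow chart of the study: the row "Adverse events" is marked at PACU, at each of D1 to D5, and at D6-discharge. It is not marked at D30.
- Section 9.1: "An adverse event indicates any unpredictable, unfavorable medical event that is associated with any medical intervention and occurs during the study period". The CRF page repeats nearly the same definition above its two questions.
- Sections 9.3 and 10.3 require adverse events and severe adverse events to be recorded and followed, with no limit on onset.

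The study period has no single meaning. Section 6.5 writes "During the study period (from preop to postop day 5"; Section 11 writes "at the completion of the study (30 days after surgery". Either reading outlasts both CRF questions.

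**The concern.** The CRF is what staff complete at the bedside. If its questions stop earlier than the protocol's window, a page can be answered truthfully and in full and still omit an in-hospital event that the protocol wants recorded. A new severe event on day 4 is properly answered No to the 3-day question; a non-severe event on day 2 or later is properly answered No to the 24-hour question.

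Staff who work from the protocol and staff who work from the CRF would then collect different data. A reader of the results could take the adverse event record to cover the hospital stay when active questioning had ended sooner. The primary delirium outcome is not affected.

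**Working it through.** No sample size or event rate enters this point. The check sets the passages side by side and counts visits.

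**1. Visits in the flow chart row.** PACU (1) + D1 to D5 (5) + D6-discharge (1) = 7 marked visits.

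**2. Visits that each CRF question reaches.**

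- 24 hours, any new event: PACU and D1, so about 2 of 7. This leaves 7 − 2 = 5 (D2, D3, D4, D5, D6-discharge). The count is generous, because part of D1 may lie beyond 24 hours.
- 3 days, new severe event: PACU, D1, D2 and D3, so 4 of 7. This leaves 7 − 4 = 3 (D4, D5, D6-discharge).

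**3. Set against planned stay.** Eligibility requires "Scheduled to stay in hospital > 3 days after surgery". Both questions therefore close before planned discharge for every eligible patient. In addition, a prolonged hospital stay is one of the criteria for a severe event in Section 10.1. With planned stays above 3 days, it will often be unclear at day 3 whether that criterion is met.

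**4. What else in the CRF would catch a later event.**

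- The Postoperative complications page runs to day 30. It lists organ, surgical and infectious complications and has blank rows for others.
- The Hospital discharge information page asks for survival and readmission to 30 days, with dates and causes.
- The severe event report form (Supplemental remark 5) has an open date of occurrence. Section 10.3 and item 10 of the CRF instructions require reporting within 24 hours, with no onset limit.
- The adverse event table itself has start and end times and blank rows, with no window printed in it.

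**5. What is left over.**

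- Events on the adverse event page that are not on the complications list. Recall is the clearest: Section 9.1 names it as a predicted event, and a patient may mention it only later. Hypotension, bradycardia, hypertension and tachycardia as defined on that page are also not listed as such, although circulatory insufficiency and treated arrhythmia are. After the windows close, these depend on someone volunteering an entry.
- Event details. Section 9.3 asks for the kind of event, when it occurred, how long it lasted, how it was managed and what followed. The adverse event table has columns for start, end, treatment, outcome and relation to the study. The complications page generally has a yes/no box and diagnostic evidence, with a time of diagnosis only in the rows for other complications. For a later non-severe event, only the adverse event table holds the full set. For a severe event, the report form holds much of it, but the only dated question that leads to that form ends at 3 days.

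**The case against.** The strongest reply is that the trial has several other routes to late harms, set out in step 4 of the working. Many events that meet the severe definition would reach the record through one of them. This stands, and it limits the point. A reader might infer from the two questions that harms after day 3 go unprompted, or that the 30-day page recovers only the complications it lists. The documents support neither: the 30-day page has open rows, and Section 7.3 gives its complication types only as examples.

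A second reply is that most of the pre-printed adverse events belong to the perioperative period. Recall refers to the time under anesthesia, and Section 9.2 manages the haemodynamic events partly by adjusting anesthetic agents. A short window may therefore lose few of them. This also has force. A reader might be tempted to spread events evenly over the postoperative days and quote a percentage missed; the documents give no onset distribution, and an even spread is implausible for these events. The visit count measures how far the questions reach, not how many events are lost.

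Third, Section 13 specifies no adverse event analysis, and the table shell in Section G is for complications, which the 30-day page supplies. No planned table can be shown to be wrong. The effect is on the completeness of the safety record.

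None of these replies explains why the CRF windows differ from Section 7.3 and the flow chart, and nothing in the documents reconciles them.

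**Conclusion.** The point holds in a limited form. The two CRF questions (24 hours; 3 days) conflict with the hospital-stay window in Section 7.3 and the flow chart, and with the absence of any onset limit in Sections 9.3 and 10.3. They leave about five of seven scheduled visits without a question on new adverse events, and three of seven without one on new severe adverse events. Both end before planned discharge in every eligible patient.

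The gap is confined to the adverse event page: events outside the complications list, and the timing, treatment, outcome and relatedness details of later events. Its size in events cannot be computed from the documents. The conclusion assumes that staff answer the questions as worded and do not routinely add later events to the untimed rows. It concerns safety data quality and should be corrected, but it does not bear on the primary comparison.

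**What to change.** - Reword the two CRF questions so that both run through hospital discharge, in line with Section 7.3 and the flow chart.
- State the same collection window for adverse and severe adverse events in Sections 9.3 and 10.3. Word it as the period of active questioning, so that it does not narrow the open-ended duty to report severe events.
- Define the study period once, since Section 6.5 ends it at postoperative day 5 and Section 11 implies 30 days, and use that meaning in Section 9.1 and on the CRF page.

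A severe event question at the existing day-30 contact is an optional, low-cost extension. The flow chart does not already require it, because its adverse event row is unmarked at D30. Starting the window at induction would likewise be an addition, because that row begins at PACU.

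The cost is two CRF lines and a few protocol sentences. The visits through discharge are already scheduled. If any patients have been followed with the present form, record which ones, so that the two sets of pages can be told apart.

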**NRS of pain severity**

(0 = no pain and 10 = the worst possible pain)

	PACU	24 hours after surgery
Score		

**Use patient-controlled analgesia pump after surgery**

 No  Yes		
 PCIA	 Morphine  Sufentanil  Others	Total dose within 24 hours:
 PCEA	 Sufentanil 125ug+1% ropivacaine 30ml)/250ml  Others	Total dose within 24 hours:

**Postoperative complications**

(Patients will be followed up until 30 days after surgery; diagnostic criteria listed in brackets)

[figure not shown]
Complications of organs/systems		Diagnostic Evidence
 Respiratory insufficiency (hypoxemia or hypercapnia, requiring mechanical ventilation for any duration after surgery)	 Yes  No	
 Pulmonary embolism (confirmed by clinical manifestations and imaging study)	 Yes  No	
 Acute myocardial infarction [increase of troponin T concentration above the hospital laboratory's myocardial infarction threshold and either new Q waves (duration of at least 0.03 seconds) or persistent changes (4 days) in ST-T segment]	 Yes  No	
 Circulatory insufficiency (requirement of inotropic agents or vasopressors for any duration after surgery)	 Yes  No	
 New onset arrhythmia (confirmed by 12-leads electrocardiography and necessitating medical treatment and/or cardioversion)	 Yes  No	
 Stroke (persisted new focal neurologic deficit and confirmed by neurologic imaging)	 Yes  No	
 Acute kidney injury (KDIGO defines AKI as any of the following: 
 
• Increase in serum creatinine by 0.3mg/dL or more within 48 hours or
 
• Increase in serum creatinine to 1.5 times baseline or more within the last 7 days or
 
• Urine output less than 0.5 mL/kg/h for 6 hours)
 
	 Yes  No	 Baseline Cr: ____  Peak Cr within 48 hours: ____  Peak Cr within 7 days: ____  Urine output: ____ mL/kg/h for ____ hours
 Deep vein thrombosis (confirmed by venous ultrasonography/venography)	 Yes  No	
 Disseminated intravascular coagulation (manifestation of abnormal bleeding, together with prolonged PT/aPTT, declined platelet/fibrinogen levels, as well as increased fibrin degradation products (including D-dimer))	 Yes  No	
 Ileus (at least one for each of the two following criteria: (1) presence of vomiting OR abdominal distension and (2) absence of flatus/stool OR not tolerating oral diet, in the absence of any precipitating complications)	 Yes  No	
Surgical complications		Diagnostic Evidence
 Wound dehiscence (wound rupture that required secondary suturing)	 Yes  No	
 Incisional hernia (requirement of secondary surgery)	 Yes	

	 No	
 Surgical bleeding (bleeding after surgery that required secondary surgical hemostasis)	 Yes  No	
 Anastomotic leakage (extravasation of contrast agent in the body cavity or retroperitoneal space that required percutaneous drainage)	 Yes  No	
 Gastrointestinal hemorrhage (decrease of hemoglobin level combined with positive occult blood test results that required treatment)	 Yes  No	
 Delayed oral intake (lack of bowel movement, flatulence, and requirement of intravenous fluid therapy for more than one week after surgery)	 Yes  No	
Infectious complications		Diagnostic Evidence
 Severe sepsis/septic shock (two or more criteria of systemic inflammatory response syndrome, with known infection and new onset dysfunction of at least one system or requirement of vasopressors to maintain blood pressure)	 Yes  No	
 Intra-abdominal abscess (confirmed by ultrasonography or CT scan and required percutaneous drainage)	 Yes  No	
 Pulmonary infection (new infiltrate on chest radiograph combined with temperature of over 38°C and leukocytosis)	 Yes  No	
 Wound infection (pus expressed from the incision, and bacteria cultured from the pus)	 Yes  No	
 Urinary tract infection (confirmed by urinalysis and urine culture and necessitated antibiotic therapy)	 Yes  No	
Other complications	Time of earliest diagnosis	Diagnostic Evidence
		
		

**Hospital discharge information**

Discharge from hospital, date (YYYY-MM-DD)	20 ____-____-____
Actual duration of hospitalization (days) based on discharge from hospital	____ days
Postoperative diagnosis (including pathological diagnosis, metastasis and tumor stage information)	
Survival at 30 days after surgery	 Yes;  No If death within 30 days, date of death: 20____-____-____ That is ____ days after surgery Cause of death:
Hospital readmissions within 30 days after surgery	 Yes;  No If readmission within 30 days, date: 20____-____-____ That is ____ days after surgery Cause of readmission:

## Supplemental remark 1. SedLine-Guided Intervention Flow Chart

**Supplemental remark 2. Mini-Mental State Examination (MMSE)  
(A Chinese version is needed.)**

**MMSE to be assessed within 48 hours before surgery and on POD 7 or before discharge.**

**Instructions: Score one point for each correct response within each question or activity.**

Patient name:			
Study sequence #:			
Date of surgery: 20__ - __ - __			
Date of the 1 st test: 20__ - __ - __; Date of the 2 nd test: 20__ - __ - __			
Maximum Score	Questions	Patient's Score	
		Pre-op	POD 5
5	“What is the year? Season? Date? Day? Month?”		
5	“Where are we now? State? County? Town/city? Hospital? Floor?”		
3	The examiner names three unrelated objects clearly and slowly, then the instructor asks the patient to name all three of them. The patient’s response is used for scoring. The examiner repeats them until patient learns all of them, if possible.		
5	“I would like you to count backward from 100 by sevens.” (93, 86, 79, 72, 65, ...) Alternative: “Spell WORLD backwards.” (D-L-R-O-W)		
3	“Earlier I told you the names of three things. Can you tell me what those were?”		
2	Show the patient two simple objects, such as a wristwatch and a pencil, and ask the patient to name them.		
1	“Repeat the phrase: ‘No ifs, ands, or buts.’”		
3	“Take the paper in your right hand, fold it in half, and put it on the floor.” (The examiner gives the patient a piece of blank paper.)		
1	“Please read this and do what it says.” (Written instruction is “Close your eyes.”)		
1	“Make up and write a sentence about anything.” (This sentence must contain a noun and a verb.)		
1	“Please copy this picture.” (The examiner gives the patient a blank piece of paper and asks him/her to draw the symbol below. All 10 angles must be present and two must intersect.)		
30	Total		

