### **4.2 Sample size calculation**

The incidence of postoperative delirium is about 14% in elderly patients who underwent laparoscopic surgery for colorectal cancer [Tei et al., 2016]. We assume that the incidence of postoperative delirium will be reduced by 1/3 in patients receiving EEG-guided care [Chan et al., 2013]. With a two-sided significance and power set at 0.05 and 80%, respectively, the sample size required to detect the reduction is 742 patients per group. Taking into account a loss-to-follow-up rate of about 5%, we plan to enroll 780 patients in each group.

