## **7. Data collection**

### **7.1 Preoperative data**

- 1) Determine patient's eligibility based on the inclusion and exclusion criteria;
- 2) Mini-mental Status Exam;
- 3) Demographic data, past medical and surgical history, medications taken at home and in hospital;
- 4) Electrocardiogram, echocardiogram if available;
- 5) Lab results.

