## 8.2 Secondary outcomes

The secondary outcomes are as follows:

- 1) Incidence of emergence delirium;
- 2) Composite complication classified as Clavien-Dindo grade II or greater within postoperative 30 days;
- 3) 24-hour postoperative nausea and vomiting (PONV);
- 4) MMSE score change;
- 5) Length of hospital stay;
- 6) Intensive care unit (ICU) admission;
- 7) 30-day hospital readmission;
- 8) 30-day all-cause mortality

Postoperative complications are as follows:

- Myocardial ischemia or infarction
- Arrhythmia requiring treatment
- Circulatory insufficiency (requiring a vasopressor or inotropic agent infusion for more than 6 hours)
- Ischemic stroke
- Hemorrhagic stroke
- Acute lung injury
- Pulmonary embolism
- Pulmonary infection requiring antibiotic treatment
- Hypoxemia or respiratory insufficiency requiring supportive treatment including intubation, CPAP, BiPAP, high-flow (>10 L/min) face mask or nasal cannula for more than 6 hours
- Acute kidney injury requiring treatment
- Urinary tract infection requiring antibiotic treatment
- Ileus
- Sepsis
- Anastomotic leakage requiring treatment
- Urinary retention requiring treatment
- Pleural or intra-abdominal effusion requiring intervention
- Wound dehiscence requiring intervention
- Bowel obstruction requiring treatment
- Deep venous thrombosis requiring treatment
- Subcutaneous emphysema requiring treatment
- Surgical bleeding or hematoma requiring intervention
- Surgical site infection (superficial or deep, but not organ or space) requiring antibiotic treatment or procedural treatment (not at bedside)
- Surgical site infection (pelvic or intra-abdominal infection or abscess, i.e., organ or space) requiring antibiotic treatment or procedural treatment (not at bedside)

- Delayed emergence requiring treatment

The Clavien-Dindo Classification (<https://www.assessurgery.com/clavien-dindo-classification/>)

Grades	Definition
Grade I	Any deviation from the normal postoperative course without the need for pharmacological treatment or surgical, endoscopic and radiological interventions Allowed therapeutic regimens are: drugs as antiemetics, antipyretics, analgetics, diuretics and electrolytes and physiotherapy. This grade also includes wound infections opened at the bedside.
Grade II	Requiring pharmacological treatment with drugs other than such allowed for grade I complications. Blood transfusions and total parenteral nutrition are also included.

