## **13. Statistical analysis**

### **13.1 General principles**

- 1) Numeric variables will be presented as mean (standard deviation) or median (minimum, maximum; or interquartile range). Categorical variables will be presented as number of cases (percentage);
- 2) Two-tailed tests will be used in all statistical analysis, and a p value of less than 0.05 will be considered to be of statistical significance for the primary outcome. The Benjamini-Hochberge procedure will be applied to control for the multiple testing for all secondary outcomes.

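### The second MMSE behind the secondary outcome of MMSE change has conflicting timing: one form gives two different days, and the study schedule and Section 7.3 list no postoperative test

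*Combined protocol and SAP*

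**What the plan says.** Section 8.2 names "MMSE score change" as the fourth of eight secondary outcomes and attaches no day to it. Section 13.1 puts it under the Benjamini-Hochberg adjustment: the "procedure will be applied to control for the multiple testing for all secondary outcomes".

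Four places bear on when the MMSE is done:

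- **MMSE form (Supplemental remark 2), instruction:** "MMSE to be assessed within 48 hours before surgery and on POD 7 or before discharge".
- **Same form, score table:** two score columns, one preoperative and one headed POD 5. The form also has fields for the date of surgery and the date of each test.
- **Section 7.1, preoperative data:** "Mini-mental Status Exam" is listed. Section 7.3, postoperative data, has eight items and none is the MMSE. Where Section 7.3 does want a timed score it says so, for example "Subjective Sleep Quality: It will be assessed at 8:00 am during the first postoperative day using the NRS".
- **Flow chart of the study:** the MMSE row is marked at screening and recruitment only. A column for day 6 to discharge exists and is blank for the MMSE.

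The case report form admits patients who are "Scheduled to stay in hospital > 3 days after surgery", so a stay that reaches POD 5 or POD 7 is not required.

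**The concern.** A change score needs two measurements at defined times. Here the second time is given as two different days on one form and is absent from the two places that staff would normally consult for scheduling. Different assessors could reasonably work to different days, and someone working from the flow chart could miss the test.

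Three things are at stake.

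- **Noise and missing data.** A mixture of test days, and some absent scores, weakens the comparison.
- **A possible link to treatment.** Length of stay is itself a secondary outcome, and Section 1 expects delirium prevention to shorten it. If test day follows discharge day and the intervention changes discharge day, the arms could be tested at different points in recovery. This matters only if MMSE scores move over those days. The documents do not say that they do, although Section 1 describes delirium as fluctuating.
- **Multiplicity.** The p-value for MMSE change is ranked with those of the other seven secondary outcomes, so a poorly measured result here can affect which of the others are declared significant.

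**Working it through.** No figure in the plan rests on the MMSE, so the check is a comparison of the texts.

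**Step 1. The plan's one computed figure, for context.** Section 4.2 starts from "The incidence of postoperative delirium is about 14% in elderly patients" and assumes that this "will be reduced by 1/3 in patients receiving EEG-guided care". With p1 = 0.14, p2 = 0.14 × 2/3 = 0.0933, mean 0.1167, two-sided alpha 0.05 and power 80%:

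n = [1.960 × √(2 × 0.1167 × 0.8833) + 0.842 × √(0.14 × 0.86 + 0.0933 × 0.9067)]² / (0.0467)² = 742 per group after rounding up.

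This matches the plan and concerns the primary outcome only. Nothing below changes it.

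**Step 2. What each source implies.** The discharge days are illustrations, not figures from the plan. The form's instruction is read as whichever event comes first, which it does not actually state.

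| Discharged on | Form instruction | Form column | Flow chart and Section 7.3 |
|---|---|---|---|
| POD 4 | by POD 4 | no test day reached, no rule given | none listed |
| POD 6 | by POD 6 | POD 5 | none listed |
| POD 9 | POD 7 | POD 5 | none listed |

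For a patient who stays beyond a week, the two readings of the one form differ by 7 − 5 = 2 days. For a patient who leaves before POD 5, the instruction gives a test and the column heading alone does not.

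**Step 3. Could the blank in the flow chart be a lost mark?** Neighbouring rows for delirium, adverse events and complications carry their postoperative marks, and Section 7.3 independently omits the MMSE. The omission looks genuine.

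**Step 4. Is a second test nevertheless required?** Yes. The form instructs it and provides a score column and a date for it. The general instructions of the case report form (item 3 under Illustration) require all pages and items to be filled in. The flow chart and Section 7.3 omit the test but do not cancel it.

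**Step 5. Does the analysis section settle the timing?** No. Under secondary endpoints, Section 13.5 gives a Wilcoxon rank sum test with a Hodges-Lehmann estimate for non-normal continuous endpoints. It names no MMSE time point, no use of the baseline score as a covariate and no treatment of varying test days.

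**The case against.** A reader might infer that no second MMSE would be collected in any of the 2 × 780 = 1,560 planned patients. The documents do not support that. It would need every assessor to follow the flow chart alone and leave a required column of the form empty.

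A reader might also infer that early discharge would systematically produce missing scores. The form's instruction provides for testing before discharge, so under it early leavers are tested sooner, not lost. The gap appears only if the POD 5 heading is read alone and rigidly.

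The other side has three further fair points. Both tests are dated on the form, so test day can be computed and examined. Section 5.2 has postoperative follow-up done by staff blinded to allocation; if they also do the MMSE, confusion over the day should fall on both arms alike, and a between-arm difference in test day would have to come through length of stay, where an effect is hoped for but not shown. And this is one of eight secondary outcomes.

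These points limit the consequences. They do not remove the contradiction. The date shows the variation after the fact but does not prevent it, and nothing in the available text says which day governs.

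**Conclusion.** The contradiction stands. The form gives two days for the second MMSE, the outcome definition gives none, and the schedule and Section 7.3 omit the test. The probable result is inconsistent test days and some missed tests in one secondary outcome.

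Neither the size nor the direction of any bias can be derived from the documents. Bias between arms would require both that the intervention shifts discharge day and that MMSE scores change over the days concerned; both are assumptions. The primary outcome, its analysis and its sample size are not touched.

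The conclusion rests on the text available for review. Some pages were not available, and a reconciling statement on one of them cannot be excluded.

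**What to change.** **Timing.** State one time point for the second MMSE in Section 8.2, Section 7.3, the flow chart, and both the instruction and the column heading of the form. One workable choice is POD 5, or the day of discharge if earlier, done at a visit already made for the delirium assessment. Say explicitly that the earlier of the two applies.

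**Remaining weakness.** This narrows the range of test days but does not make them equal. For patients who leave before POD 5, test day still follows length of stay. Use the dates already on the form to report test day by arm, and the number without a second test by arm, and check whether the result is sensitive to test day.

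**Analysis.** Keep the planned Wilcoxon and Hodges-Lehmann analysis of change. Beside it, compare postoperative MMSE between arms with baseline MMSE as a covariate. The baseline score is already collected, and adjusting for it is a low-cost gain that is useful whichever day is chosen.

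**Cost.** Wording in four places (two edits on the form), a short addition to Section 13.5, and one summary of test day by arm. If the test is tied to the delirium visit, no new visit and no new data item are needed.
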